10.4.1.1.2 Hypothesis

STAGE-12 will result in fewer positive drug screens/urinalyses than TAU.

The outcome variable will be positive drug screen (yes/no) measured at baseline, weeks 4, 8/end of treatment, 3 months and 6 months. The data will be analyzed using the proportional mean model for recurrent events (Lin et al., 2000):

$$\mu_Z(t) = E\{N_i(t) | Z_i\} = \exp(\lambda_D Z_i)\mu_0(t),$$

where Z_i = 0 if the participant belongs to TAU group and Z_i = 1 if the participant belongs to STAGE-12 group; $N_i(t)$ is the total number of positive drug screen results for participant i at the time of assessment t; λ_D is the effect of the STAGE-12 treatment. The advantage of the proportional mean model is that it does not assume the nature of the influence of prior events on the future recurrence. The following statistical hypotheses will be assessed: H_0 : λ_D =0 vs. H_1 : $\lambda_D \neq 0$. Rejection of the null hypothesis with λ_D < 0 would indicate that STAGE-12 treatment results in fewer positive drug screens than TAU. The analysis will be performed using PROC PHREG with TIE=DISCRETE option for handling ties event times and COV(AGGREGATE) option to request the robust sandwich covariate matrix estimate.

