10.4.4.1.5 Hypothesis

Individuals with higher levels of readiness to change their substance use behaviors are more likely to attend 12-step meetings and engage in 12-step activities than are those with lower levels of readiness to change.

The outcome variable will be 12-step meetings meeting attendance (yes/no). For each of the hypotheses listed above the data will be analyzed using the proportional mean model for recurrent events similar to the model for mean number of positive drug screens in 10.4.1.1.2. In this model, variable Z_i will be an indicator of a particular group of interest (e.g., ethnic minorities vs. Caucasian in the analysis for 1.3.4.1)

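### Section 10.4.1.1.2 defines the urine effect as a ratio of mean numbers of positive screens but prescribes a tie option that, with time coded by scheduled visit, estimates a per-visit odds ratio

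*Protocol*

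**What the plan says.** Section 10.4.1.1.2 of the protocol sets out the urine analysis in four steps.

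- **Outcome.** "The outcome variable will be positive drug screen (yes/no) measured at baseline, weeks 4, 8/end of treatment, 3 months and 6 months".
- **Model.** "The data will be analyzed using the proportional mean model for recurrent events (Lin et al., 2000"), written as E{N_i(t) | Z_i} = exp(λ_D Z_i) μ_0(t), where Z is 1 for STAGE-12 and 0 for TAU, and N_i(t) "is the total number of positive drug screen results for participant i at the time of assessment t".
- **Fitting.** "The analysis will be performed using PROC PHREG with TIE=DISCRETE option for handling ties event times", together with the "COV(AGGREGATE) option to request the robust sandwich covariate matrix estimate".
- **Decision rule.** A two-sided test of λ_D = 0; rejection with a negative λ_D "would indicate that STAGE-12 treatment results in fewer positive drug screens than TAU".

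Section 10.4 lists the urine screen fifth of six key secondary endpoints, makes no multiplicity adjustment and treats significant findings as exploratory. For the client-subtype hypotheses on meeting attendance, section 10.4.4.1.5 says "the data will be analyzed using the proportional mean model for recurrent events similar to the model for mean number of positive drug screens". It does not repeat the tie option.

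**The concern.** The formula and the software option in the same section do not estimate the same thing. Under the formula, exp(λ_D) compares mean counts: 0.80 means 20% fewer positive screens. The discrete tie option is not an approximation to that model for tied data. It substitutes a logistic model for the probability of a positive result at each event time, and its coefficient is a log odds ratio. The two agree when positives are rare at each event time and separate as they become common.

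What is at stake is the size and label of the estimate. A reader who takes exp(λ_D) as the section defines it would read an odds ratio as a proportional reduction in positive screens. The urine screen is the objective measure in a trial whose primary outcome is self-report, so its effect size is likely to be looked at even though the endpoint is exploratory.

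**Working it through.** The protocol states no positivity rate, effect size or power for this endpoint, so there is no figure of its own to reproduce.

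**Inputs.** From the protocol: the model formula, the meaning of N(t), the fixed visits and the tie option (10.4.1.1.2); about 200 per arm, 70% retention and a correlation of 0.5 (10.6; the correlation is stated for the primary outcome and is borrowed here as a latent correlation). Assumed: positivity per visit in TAU, p0, varied over a range; a true mean ratio R of 0.80 or 0.75; time coded by scheduled visit.

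**Step 1: what each option solves.** At a visit let n1 and n0 be the numbers at risk in STAGE-12 and TAU, d1 and d0 the positives, and d = d1 + d0.

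- Breslow: Σ [d1 − d·n1·e^b / (n1·e^b + n0)] = 0. With everyone at risk at every visit this gives e^b = (Σd1/n1) / (Σd0/n0), exactly the ratio of mean counts.
- Discrete: Σ [d1 − E(d1 | d, b)] = 0, where the expectation is that of a non-central hypergeometric distribution. This is conditional logistic regression stratified by visit, so e^b is a common odds ratio.

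**Step 2: the odds ratio implied by a mean ratio of 0.80.** With p1 = 0.80·p0, OR = [p1/(1 − p1)] / [p0/(1 − p0)].

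| p0 | p1 | Calculation | OR | Reduction if read as a mean ratio (true 20%) |
|---|---|---|---|---|
| 10% | 8% | (0.08/0.92)/(0.10/0.90) | 0.783 | 22% |
| 20% | 16% | (0.16/0.84)/(0.20/0.80) | 0.762 | 24% |
| 40% | 32% | (0.32/0.68)/(0.40/0.60) | 0.706 | 29% |
| 60% | 48% | (0.48/0.52)/(0.60/0.40) | 0.615 | 38% |

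**Step 3: simulation with scheduled-visit times.** With 200 per arm, four post-baseline visits, latent correlation 0.5, R = 0.80 and 200 replicates, a visit-stratified logistic fit gave 0.771, 0.708 and 0.616 at 20%, 40% and 60% positivity. Breslow gave 0.808, 0.801 and 0.801. A separate calculation solved the exact conditional score with 70% final retention and R = 0.75 (500 replicates). Discrete against Breslow was 0.736 and 0.756 at 10%, 0.679 and 0.751 at 30%, and 0.603 and 0.751 at 50%.

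**Step 4: no effect.** At R = 1 in the same set-up the two options gave 0.981 and 0.983 at 10%, 1.001 and 1.001 at 30%, and 1.005 and 1.002 at 50%. There is no distortion under the null hypothesis.

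**Step 5: actual dates instead of visits.** With R = 0.80 and assessment days spread ±3 days around each visit (an assumed width; 25 replicates), Breslow against discrete was 0.787 and 0.782 at 20%, 0.786 and 0.776 at 40%, and 0.800 and 0.786 at 60%. With ±7 days the difference was at most 0.01. Few positives then share a day, and the two options nearly coincide.

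**Step 6: counting the baseline screen.** The section lists baseline among the measurements. With 50% positive at baseline, 30% in TAU at follow-up and a follow-up ratio of 0.75, discrete gave 0.759 and Breslow 0.836. Both move towards 1, and the discrete estimate stays further from it.

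**The case against.** The strongest reply is that nothing fixes t as the nominal visit. Section 10.4.1.1.2 speaks of the time of assessment, and section 5.1.4 says participants are followed within visit windows, so real dates will differ. Step 5 shows that the discrete option then does little harm. This stands, and it makes the size of the problem conditional on how time is coded. It does not remove the mismatch: the section lists a few common assessment times and expressly plans for ties, which makes scheduled-visit coding the more natural reading. Breslow matches the stated model under either coding.

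A second reply is that the section uses λ_D only for a test and a sign rule and promises no effect estimate. This also stands as far as it goes: neither the test nor the rule is harmed. A reader might infer that the urine test is invalid or that a false positive becomes more likely; step 4 gives no support for that.

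A third reply concerns 10.4.4. A reader might infer that every subtype analysis is wrong. The text says only that the model is similar and does not carry over the tie option. The Substance Use Calendar also records attendance by day (5.4.2.1), so event times there could be much finer than visits. The mismatch reaches 10.4.4 only if the same option is applied to visit-level data.

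**Conclusion.** The section is internally inconsistent: the formula defines a ratio of mean counts, and the tie option belongs to a discrete logistic model. With time coded by scheduled visit, the estimate is a per-visit odds ratio: for a true mean ratio of 0.80, about 0.78 at 10% positivity and 0.62 at 60%. The gap is small at 10% positivity or below and material from about 30% upwards.

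A reader might go further and conclude that the reported urine effect will be badly overstated. The protocol does not support that as a certainty. It would take visit-level time coding, a high positivity rate and an exp(λ_D) reported as a mean ratio, and the protocol settles none of the three. What holds is narrower: the plan as written can yield an estimate that is not the quantity it defines, on an exploratory secondary endpoint. The hypothesis test, the sign rule and the primary analysis are essentially untouched.

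**What to change.** In 10.4.1.1.2, replace TIE=DISCRETE with TIES=BRESLOW and keep the aggregated robust sandwich variance. State whether t is the scheduled visit or the actual assessment date. Make the same change in 10.4.4 wherever the discrete option would be applied.

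Alternatively, keep the discrete option, define the effect as a per-visit odds ratio, label it so in the results, and remove the mean-model formula.

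Either route costs one program option or a sentence or two of text, with no change to data collection or trial conduct. Under the first route, with visit-level coding, any estimated effect will be less extreme.

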10.4.1.1.3 Hypothesis

STAGE-12 will result in lower scores on the ASI Drug and Alcohol Composite Scores than TAU.

The outcome variable will be ASI Drug and Alcohol Composite Scores assessed at baseline, week 8/end of treatment, 3 months and 6 months. The data will be analyzed using a hierarchical linear model similar to the model for the primary outcome. Let α_S denote the effect of the STAGE-12 treatment in the Level-2 model. The hypotheses H₀: α_S =0 vs. H₁: α_S ≠0 will be evaluated and rejection of the null hypothesis with α_S < 0 would indicate that STAGE-12 treatment results in lower ASI Drug and Alcohol Composite Scores than TAU.

10.4.2 12-Step Outcomes

10.4.2.1 Objective

To evaluate the degree to which a brief, combined group-plus-individually delivered 12-step facilitative intervention, integrated into treatment as usual, increases involvement in 12-step activities, meeting attendance, and acceptance of 12-step beliefs and values, compared to TAU.

10.4.2.1.1 Hypothesis

STAGE-12 will result in greater 12-step attendance (attend more meetings) than TAU

The outcome variable will be percent of days (frequency) of the 12-step meeting attendance in the SUC over the assessment window, measured at baseline, weeks 4, 8/end of treatment, 3 months and 6 months. The data will be analyzed using a hierarchical linear model similar to the model for the primary outcome. Let α_{AA} denote the effect of the STAGE-12 treatment in the Level-2 model. The hypotheses H₀: α_{AA} =0 vs. H₁: α_{AA} ≠0 will be evaluated and rejection of the null hypothesis with α_{AA} > 0 would indicate that STAGE-12 treatment results in greater levels of 12-step meeting attendance than TAU.

10.4.2.1.2 Hypothesis

STAGE-12 will result in greater levels of 12-step activities than TAU.

The outcome variable will be percent of days (frequency) of the behaviors addressed in the SHAQ over the assessment window, measured at baseline, weeks 4, 8/end of treatment, 3 months and 6 months. The data will be analyzed using a hierarchical linear model similar to the model for the primary outcome. Let α_{ACT} denote the effect of the STAGE-12 treatment in the Level-2 model. The hypotheses H₀: α_{ACT} =0 vs. H₁: $\alpha_{ACT} \neq 0$ will be evaluated and rejection of the null hypothesis with $\alpha_{ACT} > 0$ would indicate that STAGE-12 treatment results in greater levels of 12-step activities than TAU.

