5.4.3.2.2 Self-Help Activities Questionnaire (SHAQ)

The SHAQ is a self-report instrument which will be administered at all research visits, that was developed for use in the NIDA Cocaine Collaborative Treatment Study. It assesses the frequency of attendance at a number of self-help groups (both 12-step – e.g., AA, NA, CA, CMA and non-12-step – e.g., Rational Recovery, Secular Organization for Sobriety) and the degree of participation in self-help activities in each of these groups (Weiss, Griffin et al. 1996). At each assessment, participants are asked to indicate whether they have an AA/NA/CA sponsor. They are also asked how many days in a given time period that they attended Speaker meetings and Step meetings (e.g., attendance measures), how many days that they have attended meetings in which they have had duties (e.g., setting up, making coffee), spoken at meetings, met with sponsors or other group members outside of the meetings, phoned or have been phoned by sponsors or other group members, read 12-step recovery literature, and worked on any of the steps (e.g., measures of participation). The original time frame was a week, so that subjects indicated the frequency of these behaviors from 0 to 7. Measures of internal consistency reliability were high (Cronbach alpha ranging from .78 to .85) for AA, NA, and CA items. Factor analyses resulted in three primary factors: "work performed at meetings,"

"interpersonal work performed outside of meetings," and "work performed alone and outside of meetings." The measure has been used to describe self-help related behaviors (Weiss, Griffin et al. 1996), to evaluate differential changes in these behaviors as a function of the type of treatment received (Weiss, Griffin et al. 2000), and to compare the relationship between 12-step attendance and participation with subsequent drug use outcomes (Weiss, Griffin et al., 2005).

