- 2. Second Individual Session: The second session content will vary, depending on whether the participant has attended a 12-step meeting since the first session. If so, the participant's reactions to the meeting will be discussed and homework will be reviewed. If not, the session will focus on perceived and actual barriers to attendance and a 12-step meeting volunteer will again be contacted.
- 3. Third Individual Session: The third session will involve reviewing recovery assignments and participant experiences. The session will be focused on reviewing views of addiction and 12 step programs now as opposed to prior to treatment. It will either focus on finding a sponsor if a meeting was attended since the last session or setting up a meeting with a 12-step group volunteer if a meeting was not attended. Barriers to participation will be reviewed. Goals and plans for the future will be discussed.

An important component of STAGE-12 intervention is the work done outside of sessions. Both group and individual sessions have "homework" that the participant is asked to complete between sessions and be ready to share in the group or with the counselor. There are four elements to this homework. The first is literature (e.g., AA's Big Book, NA's Basic Text) that clients are asked to read. This material is meant to complement the topics discussed during the weekly sessions. The second is "recovery tasks," which the participant is asked to do, such as contacting a sponsor, taking on service work at a meeting, etc. The third is strong encouragement from the counselor to attend several different kinds of 12-step meetings per week. The final element is keeping a journal. The journal

documents 12-step group attendance and participation, reactions to the meetings and other assigned recovery tasks, or, if the client did not attend a meeting, what factors served as barriers to attendance. They are also asked to keep track of when, where, and with whom they experienced urges to use drugs or actual slips, how they handled these, and what they could do in the future (e.g., calling a 12-step friend, going to a meeting, going to a 12-step group social activity, calling one's sponsor). The journal entries are reviewed at the beginning of each individual session, while the other activities are reviewed during the check-in at group session. These activities provide additional material for the weekly sessions.

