10.4 Secondary Outcomes

Key secondary endpoints are listed below in order of priority. No adjustment for multiplicity of the comparisons will be made and any statistically significant findings will be treated as exploratory.

- 1. Substances use other than stimulants (including alcohol) derived from Substance Use Calendar
- 2. 12-step meeting attendance derived from Substance Use Calendar
- 3. 12-step meeting attendance derived from Self-Help Activities Questionnaire
- 4. Involvement in 12-step activities derived from Self-Help Activities Questionnaire
- 5. Urine drug screen
- 6. Alcohol and Drug Use Composite Scores derived from the ASI

Other secondary endpoints should be considered as exploratory.

The following data analytic methods will be used to test hypotheses related to these secondary endpoints.

- a. Hierarchical linear modeling will be used to assess the following endpoints:
 - 1. % of days of non-stimulant use over assessment window (via Substance Use Calendar)
 - 2. % of days of 12-step meeting attendance
 - 3. Involvement in 12-step activities
 - 4. ASI Drug and Alcohol composite Scores
 - 5. Spirituality derived from the Spiritual Involvement and Beliefs Scale
 - 6. Perceived barriers to 12-step involvement derived from the Survey of Readiness for Alcoholics Anonymous Participation
- b. The proportional mean model will be used to assess these endpoints:
 - 1. Positive drug screen from urinalysis

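### The 12-step activities outcome in 10.4.2.1.2 is worded more broadly than involvement: read as written, it includes the SHAQ attendance items and non-12-step groups

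*Protocol*

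**What the plan says.** Section 10.4.2.1.2 states the hypothesis as "STAGE-12 will result in greater levels of 12-step activities than TAU" and defines its outcome in one sentence: "The outcome variable will be percent of days (frequency) of the behaviors addressed in the SHAQ over the assessment window". It then tests a single coefficient for the treatment effect.

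Section 5.4.3.2.2 describes the instrument. On scope, "It assesses the frequency of attendance at a number of self-help groups (both 12-step" and non-12-step organisations alike; the sentence continues with "Rational Recovery, Secular Organization for Sobriety) and the degree of participation in self-help activities in each of these groups". Among the items, participants report "how many days in a given time period that they attended Speaker meetings and Step meetings (e.g., attendance measures". Six further behaviours follow, and the protocol labels these as measures of participation. The recall window is 30 days at every research visit.

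The ranked list in section 10.4 has SHAQ meeting attendance in third place and, as a separate fourth endpoint, "Involvement in 12-step activities derived from Self-Help Activities Questionnaire". Section 10.4.3.1.1 tests attendance and activities as alternative mediators of substance use. Section 10.4 also says that there is no multiplicity adjustment and that significant secondary findings are exploratory.

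**The concern.** The protocol's rationale depends on keeping attendance and involvement apart. Section 3.3 reports that involvement is the better predictor of substance use outcomes, and section 3.8 adopts the position that one cannot stand in for the other. The endpoint list and the mediation plan follow that distinction. The outcome definition in 10.4.2.1.2 does not.

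An analyst who applies the sentence as written would put the two attendance items, and behaviours in groups outside the 12-step fellowships, into the score used to claim an effect on involvement. Two results would then be harder to interpret:

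- **Endpoint 4.** A treatment effect confined to meeting attendance would show up partly as an effect on activities.
- **The mediation analysis.** Section 10.4.3.1.1 gives the activities mediator no definition of its own, so 10.4.2.1.2 is its natural source. The attendance and activities mediators would then share content by construction, which weakens any statement about which of the two matters.

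**Working it through.** The protocol gives no figure for this endpoint, so there is nothing to reproduce. The check is a comparison of sections followed by short arithmetic.

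**1. Which behaviours does the SHAQ address?** From 5.4.3.2.2, the items reported as numbers of days are:

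| Protocol's own class | Items | Count |
|---|---|---|
| Attendance | Speaker meetings; Step meetings | 2 |
| Participation | duties at meetings; speaking; meeting a sponsor or members outside; phoning; reading; step work | 6 |

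That makes 2 + 6 = 8 day-count items. Having a sponsor is asked as yes/no and is not a day count.

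**2. Does the phrase in 10.4.2.1.2 exclude any of them?** It does not. Elsewhere the protocol uses nearly the same phrase broadly. The outcome paragraph that closes 10.4.3.1.4, which serves hypotheses about attendance and involvement together, refers to the behaviours in the SUC, SHAQ and ITSI. The wide reading is therefore the natural one.

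**3. Does the wide reading fit the rest of the plan?** It conflicts with the separate third and fourth endpoints in 10.4, with the separate mediators in 10.4.3.1.1, and with the hypothesis itself, which names 12-step activities only.

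**4. How much could it matter?** The protocol states no combination rule. I assume one item per behaviour and an equal-weight mean:

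Score (%) = 100 × (sum of the 8 day counts) / (8 × 30)

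- Weight of attendance: 2/8 = 25%. Weight of participation: 6/8 = 75%.
- Suppose attendance rises by g days on each of its two items and participation does not change. The score then rises by 100 × 2g / 240. The value of g is an assumption, so a range is shown:

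| g (days per attendance item) | Apparent gain, 8-item mean | Gain, 6 participation items only |
|---|---|---|
| 2 | 100 × 4/240 = 1.7 points | 0 |
| 4 | 100 × 8/240 = 3.3 points | 0 |
| 8 | 100 × 16/240 = 6.7 points | 0 |

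- The reverse also holds. If participation rises by 4 days on each of six items and attendance does not change, the six-item mean rises by 100 × 24/180 = 13.3 points but the eight-item mean by only 100 × 24/240 = 10.0 points. The true involvement effect is diluted to 75% of its size.

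**5. Non-12-step groups.** The documents give no frequency of attendance at these groups, so their contribution cannot be sized.

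**The case against.** The strongest reply is that a fair reader can recover the intended meaning. Section 5.4.3.2.2 labels which items are attendance and which are participation, 10.4 lists the two endpoints separately, 10.4.2.1.1 takes attendance from the Substance Use Calendar, and the hypothesis in 10.4.2.1.2 names activities. Several SHAQ items are specific to 12-step groups by their wording. Item scoring is commonly left to the SAP, which is not at hand. Attendance is also analysed separately, so an attendance effect would be visible next to the activities result.

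Much of this stands. The intent is recoverable, the missing combination rule is not a finding, and the impact is limited. It does not remove the point, because 10.4.2.1.2 does not leave the content open. It states an outcome that is wider than its construct, and an SAP limited to participation items would depart from that text.

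Three stronger readings are tempting but not supported:

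- **That the item counts are added, so the percentage can exceed 100.** Nowhere does the protocol say this. A mean, item-by-item analysis or factor scores fit the text equally well, and a mean cannot exceed 100%.
- **That overlapping counts inflate the STAGE-12 arm more than TAU,** because those participants receive "strong encouragement from the counselor to attend several different kinds of 12-step meetings per week". As a double-counting argument this depends on summing, which is not stated.
- **That the endpoint does not measure involvement.** Six of the eight day-count items are participation measures.

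The yes/no sponsor item is likewise no contradiction. It cannot enter a day-based score, but nothing prevents its separate analysis.

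**Conclusion.** The point holds as a mismatch between wording and construct. As written, the outcome in 10.4.2.1.2 takes in items labelled "attended Speaker meetings and Step meetings (e.g., attendance measures" and behaviours in non-12-step groups, while the plan elsewhere keeps attendance and involvement apart.

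The 25% weight and the 3.3-point apparent gain rest on three assumptions: one item per behaviour, an equal-weight mean, and 4 extra days on each attendance item with participation unchanged. None of these is stated in the protocol, so the figures indicate scale and do not predict a bias.

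The consequence is confined to a key secondary endpoint declared exploratory and to the mediation analysis that draws on it. The primary outcome and the sample size are untouched.

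**What to change.** In 10.4.2.1.2, replace the reference to all SHAQ behaviours with the six participation items of 5.4.3.2.2 (duties, speaking, meeting a sponsor or members, phoning, reading, step work), counted for 12-step fellowships only. Use the same definition for the activities mediator in 10.4.3.1.1. State that the Speaker and Step meeting items are analysed only under endpoint 3 of section 10.4.

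The rule for combining items and fellowships can be given in the same sentence or left to the SAP. Duties and speaking take place at meetings, so the restricted score will still depend somewhat on attendance. That follows from the protocol's own classification of the items and is no reason to keep the wider wording.

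The cost is a few words in two sections. No new data, visits or change to the sample size are needed.
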